6.3 MEASURES TO MINIMIZE BIAS: RANDOMIZATION AND BLINDING

Randomization: The randomization scheme will assign patients into four groups to receive vitamin E at 133.4 mg (200 IU), 266.8 mg (400 IU), or 533.6 mg (800 IU) or placebo daily. The randomization design will be stratified by clinical center with assignments in permuted blocks of random length within each clinic. This scheme will ensure that the four groups will be balanced by calendar time of randomization (to minimize secular effects) and by clinic (to minimize clinic-specific effects of differences in patient populations and management).

The randomization plan will be prepared and administered centrally by the Data Coordinating Center (DCC) but will not require real time interaction with a DCC staff member. Requests for randomizations will be made by the clinics using a web-based application. An assignment will be issued only if the database shows that the patient is eligible, has signed the consent statement, and has had all required baseline data keyed into the database.

Treatment assignments are double masked throughout the study until all data collection for the VEDS trial has been completed (i.e., after completion of the post-trial follow-up for all participants). Every effort will be made to maintain the masking throughout the study except in emergencies. The code of specific pharmacological treatment will not be broken without the knowledge of the clinical center's principal investigator and the study leadership.

Unmasking of study medication may occur under the following conditions:

- **Severe allergic reaction (Stevens-Johnson Syndrome):** Study medication is stopped indefinitely. The patient, primary care provider (PCP), and the investigator may be unmasked.
- **Pregnancy during the study:** Study medication will be stopped indefinitely, and the coded medication may be unmasked. The patient, PCP, and investigator will be notified of the associated risks of teratogenicity.
- **Development of hepatotoxicity:** The drug induced liver injury (DILI) criteria described in section 7.1 will be used to define hepatotoxicity for this study. Study medication will be discontinued; however, there will be no unmasking until study conclusion.
- **Development of serious bleeding:** Serious bleeding will be defined as bleeding associated with a serious adverse event (SAE) (see section 8.3.2). The patient, primary care provider (PCP), and the investigator may be unmasked.

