7 STUDY INTERVENTION DISCONTINUATION AND PARTICIPANT DISCONTINUATION/WITHDRAWAL

7.1 DISCONTINUATION OF STUDY INTERVENTION

If the participant is in the treatment phase of the trial, and he/she develops a treatment related CTCAE v5.0-defined adverse event grade 3 or above, the medication will be stopped and the participant assessed by the site study investigator who is a licensed physician/hepatologist. If the adverse event was severe, prolonged, or in the view of the investigator the participant is intolerant of the medication, the study drug will be stopped and the participant will no longer receive the study medication, but will continue to be followed in the study according to the protocol, in keeping with the "intention-to-treat" paradigm.

Participants will be monitored for drug induced liver injury and will use the scale below to grade the adverse effects*:

	Grade 1	Grade 2	Grade 3	Grade 4
ALT	BSL elevated: 3x BSL or >400 U/L	BSL elevated: >3-5x BSL	BSL elevated: >5 -20x BSL	BSL elevated: >20x BSL
AST	BSL nl:3 x ULN BSL elevated: 3x BSL	BSL nl:>3-5 x ULN BSL elevated: >3-5x BSL	BSL nl:>5-20 x ULN BSL elevated: >5-20x BSL	BSL nl:>20 x ULN BSL elevated: >20x BSL
Total Bilirubin	1.5 x ULN	>1.5-3.0 x ULN	>3.0-10.0 x ULN	>10.0 x ULN

Any participant found to meet the above criteria for grade 2 or higher drug induced liver injury will have the study medication stopped pending further study investigator evaluation.

In addition, participants will have the study medication stopped if **ANY** of the following occur[81]:

If normal baseline AST:

- AST value $>5 \times \text{ULN}$ in two repeat tests (within 14 days); OR
- AST value is $>8 \times \text{ULN}$; **OR**
- AST value $>5 \times \text{ULN}$ AND total bilirubin $>2 \times \text{ULN}^\ddagger$ OR presence of symptoms suggesting liver injury (severe fatigue, nausea, vomiting or right upper quadrant pain),

If elevated baseline AST or ALT:

- ALT or AST value $>3 \times \text{BSL}$ or 300 U/L in two repeat tests (within 14 days); OR
- ALT or AST value $>5 \times \text{BSL}$ or $>500 \text{ U/L}$ (whichever occurs first); OR
- ALT or AST value $>3 \times \text{BSL}$ or $>300 \text{ U/L}$ (whichever occurs first) AND total bilirubin $>2 \times \text{ULN}^\ddagger$ OR presence of symptoms suggesting liver injury (severe fatigue, nausea, vomiting, or right upper quadrant pain)

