Follow-up visits will continue, but the study medication will not be restarted. The participant will be included in intention-to-treat analyses.

Additionally, if a participant is found to have signs of increased bleeding (i.e. petechiae) on physician assessment or a participant reports any signs of increased bleeding (i.e. bleeding gums), the study medication will be discontinued until the participant can be further examined by a study physician. The study medication may be restarted after further examination if the bleeding was not associated with a serious adverse event (CTCAE grade 3 or higher) and if the study physician deems a re-challenge appropriate.

* Values for ULN are defined at each clinical center per laboratory guidelines.

‡ For participants with suspected Gilbert's Syndrome at baseline: doubling of direct bilirubin

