8.3.2 DEFINITION OF SERIOUS ADVERSE EVENTS (SAE)

An adverse event (AE) or suspected adverse reaction is considered "serious" if, in the view of either the investigator or sponsor, it results in any of the following outcomes: death, a life-threatening adverse event, inpatient hospitalization or prolongation of existing hospitalization, a persistent or significant incapacity or substantial disruption of the ability to conduct normal life functions, or a congenital anomaly/birth defect. Important medical events that may not result in death, be life-threatening, or require hospitalization may be considered serious when, based upon appropriate medical judgment, they may jeopardize the participant and may require medical or surgical intervention to prevent one of the outcomes listed in this definition. Examples of such medical events include allergic bronchospasm requiring intensive treatment in an emergency room or at home, blood dyscrasias or convulsions that do not result in inpatient hospitalization, or the development of drug dependency or drug abuse.

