8.3.5 ADVERSE EVENT REPORTING

Adverse events will be recorded on study data forms whether or not they are thought to be associated with the study or with the study drug. Adverse events may be discovered during regularly scheduled visits or through unscheduled patient contacts between visits.

Summary data on adverse events will be monitored by the DSMB quarterly and at its semiannual meetings or more frequently, as needed. These summaries will include analyses comparing rates of adverse events by treatment group, by clinic, or in other subgroups requested by the DSMB. Where applicable, signs and symptoms associated with the adverse event will be graded as to severity by the clinical site staff as mild, moderate, or severe using Version 5.0 of the National Cancer Institute's Common Terminology Criteria for Adverse Events (CTCAE).[82]

After each DSMB meeting, the NIDDK will issue a written summary of the review of the study data, including adverse events, for transmission to the sIRB. Analyses or listings of adverse events will not be provided to the sIRB; however, adverse events involving unanticipated problems involving risks to patients, or breaches of protocol which might entail risk to patients must be reported to the sIRB and, as required, to the local IRB as soon as possible after they are discovered. Each participating center is responsible for ensuring that all sIRB and local IRB requirements for reporting adverse events are met.

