8.3.6 SERIOUS ADVERSE EVENT REPORTING

Serious adverse events (SAE) must be reported upon discovery at the clinical center. This will involve completing a data form describing the severity and details of the event, which must be submitted to the Data Coordinating Center within one business day for review by the Safety Officer.

If the SAE is **unexpected AND there is a reasonable possibility that the study drug caused the SAE**, then the clinical center must complete a data form for an IND Safety Report and submit it along with a narrative and a copy of the IRB report to the DCC. The DCC will submit a preliminary report to the NIDDK Program Official, Project Scientist and the NIDDK Regulatory Affairs Specialist for review within three business days of receiving the SAE data form. The study drug manufacturer will also be notified within 7 days of the serious adverse event, if applicable. If NIDDK determines that the SAE requires an expedited IND Safety Report, the NIDDK Program Official or the NIDDK Regulatory Affairs Specialist will notify the FDA no more than 15 calendar days from the initial receipt of the SAE by the DCC (no later than 7 calendar days if the SAE is fatal or life threatening). The clinical center investigator may also be responsible for completing an FDA MedWatch 3500 form and additional information for a follow-up SAE report as information becomes available. If the FDA determines that a change to the Investigator's Brochure (IB), IND, or protocol is needed, the Data Coordinating Center will send a copy of the IND Safety Report to all clinical centers, with instructions to forward the report to their IRB.

The DCC will maintain a list of all SAEs for reporting and review at Steering Committee meetings and DSMB meetings. The DSMB will review each SAE report. If requested by any member of the DSMB, a teleconference will be scheduled to discuss the SAE and recommend any actions to the NIDDK sponsor. The clinical center must submit to the NIDDK and to the Data Coordinating Center a follow-up memo within one month of the SAE (and periodic updates if needed) to report the details of the disposition of the SAE.

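### The restart rule after bleeding in section 7.1 equates a serious adverse event with CTCAE grade 3 or higher, so a bleed that is serious under section 8.3.2 but graded lower can be read as eligible for re-challenge

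*Combined protocol and SAP*

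**What the plan says.** Section 7.1 interrupts study drug when a participant shows or reports signs of increased bleeding, until a study physician has examined the participant. Drug may then restart on two conditions, both required. The first is "if the bleeding was not associated with a serious adverse event (CTCAE grade 3 or higher"). The second is "if the study physician deems a re-challenge appropriate".

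Four other places bear on the first condition:

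- **Section 8.3.2** defines a serious adverse event by outcome (death, threat to life, hospital admission or a longer stay, incapacity, birth defect), in the view of the investigator or the sponsor. It adds a limb based on judgment: "Important medical events that may not result in death, be life-threatening, or require hospitalization may be considered serious" when medical judgment supports it. No CTCAE grade appears.
- **Sections 8.3.3.1 and 8.3.5** deal with severity. The first notes that a severe event is not necessarily a serious one. The second has events "graded as to severity by the clinical site staff as mild, moderate, or severe using Version 5.0" of CTCAE.
- **Section 6.3**, on unmasking, states: "Serious bleeding will be defined as bleeding associated with a serious adverse event (SAE) (see section 8.3.2"). It mentions no grade.
- **The opening of section 7.1** has a general stop. If a participant "develops a treatment related CTCAE v5.0-defined adverse event grade 3 or above, the medication will be stopped" and the participant is assessed. The stop becomes permanent on a further condition: "If the adverse event was severe, prolonged, or in the view of the investigator the participant is intolerant of the medication".

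**The concern.** The bracket reads as a definition, but it defines seriousness by a severity grade, which the protocol elsewhere treats as a different property. A site that follows the bracket and a site that follows 8.3.2 can reach different answers on whether the same participant may be re-challenged.

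Bleeding is a named risk of vitamin E (section 2.3.1), and section 8.2 has it evaluated throughout the study. The first condition is meant to settle some cases before the physician's judgment comes in, so it should have one meaning. As written, a bleed could count as serious for unmasking under 6.3 and still be eligible for restart under 7.1.

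**Working it through.** The plan gives no figure on this point and no arithmetic applies. The check sets the texts side by side.

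**Step 1. Define the two properties.** Let S mean that the bleeding was associated with an event that is serious under 8.3.2. Let G mean that it was associated with an event of CTCAE grade 3 or higher, the bleed itself included. Nothing in the documents says that either implies the other, and 8.3.3.1 indicates that they can differ.

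**Step 2. List the readings of the first condition.** The bracket can replace the term (restart barred if G). The term can keep its 8.3.2 meaning (barred if S). The bracket can also be taken to narrow the term to serious events that are, in addition, grade 3 or higher (barred if S and G).

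| Case | Bracket reading | 8.3.2 reading | Narrowed reading | Proposed wording (S or G) |
|---|---|---|---|---|
| S and G | barred | barred | barred | barred |
| S, not G | eligible | barred | eligible | barred |
| G, not S | barred | eligible | eligible | barred |
| neither | eligible | eligible | eligible | eligible |

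Eligible means that the first condition is met and the study physician must still agree. The table takes this condition alone; steps 3 and 4 add the rest of 7.1.

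**Step 3. Serious but below grade 3.** The general stop in 7.1 starts at grade 3, and its permanent stop refers back to the same event, so neither reaches this case. Under the bracket only the study physician's judgment stands between the participant and re-challenge. The clearest route into this case is the important-medical-event limb of 8.3.2, which turns on judgment and not on a grade.

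**Step 4. Grade 3 or higher but not serious.** If the bleed is judged related to treatment, the general stop applies, and it becomes permanent if the event was severe or prolonged or the drug is not tolerated. Section 9.4.4 orders severity as none, mild, moderate, severe, life-threatening. If grade 3 corresponds to severe, which that order suggests but no section states, the permanent stop would normally follow. What remains is mainly bleeds judged unrelated, which the general stop does not cover.

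**Step 5. Look for a reconciling text.** Neither 6.3, 7.1 nor 8.3 says that, for bleeding, grade 3 stands in for the 8.3.2 definition.

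**The case against.** The strongest reply is that 7.1 supplies its own criterion. Unlike 6.3, it does not point to 8.3.2, and its threshold matches the grade 3 rule that opens the section. A site would most naturally apply the grade, so divergence between sites is possible but not shown. That is fair. It does not remove the problem, because on that natural reading a bleed that 6.3 calls serious is eligible for re-challenge.

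A second reply is that other safeguards exist. Restart is optional under every reading and needs the physician's agreement. A physician who thinks an event may jeopardize the participant will usually not re-challenge, although 8.3.2 also lets the sponsor call an event serious. Section 7.2 allows withdrawal in the participant's interest. Section 8.3.6 sends serious events to the Safety Officer and states: "The DSMB will review each SAE report". All of this stands and limits the consequence. None of it says what the first restart condition means.

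A third reply is that a bleed both serious and below grade 3 may never occur. The CTCAE v5.0 bleeding grades are not in the documents, so this can be neither confirmed nor ruled out.

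A reader might infer that the plan sends participants back on drug after serious bleeding. It does not: it leaves one class of bleeds eligible, subject to judgment. A reader might also infer that the reverse gap is equally wide, but the general stop covers most of it. Nor is the bracket and 8.3.2 readings' disagreement in two of the four cases a measure of size, since any two criteria that can vary independently would show the same pattern.

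**Conclusion.** Wrong as written: a minor internal inconsistency in a safety rule. The mismatch between the bracket in 7.1 and the definition in 8.3.2 rests on the text alone and is certain. The main consequence is that, read by the bracket, bleeding that is serious under 8.3.2 but graded below 3 is eligible for re-challenge on the study physician's judgment alone. The reverse case is mostly confined to bleeds judged unrelated to treatment.

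No frequency can be attached to either case. Alpha, power and the primary analysis do not change. The documents do not support treating this as a flaw in the trial's design, and they do not show which criterion the sponsor intended.

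**What to change.** In 7.1, replace the first condition so that restart is allowed only when the bleeding was associated with neither a serious adverse event as defined in section 8.3.2 nor any adverse event of CTCAE grade 3 or higher. Keep the study physician's agreement as the second condition. Leave 6.3 and 8.3.2 as they are.

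This wording gives one answer in every case and releases no case that any of the three readings would bar. It is the conservative union, and it is stricter than either the grade or the 8.3.2 definition alone, so it goes beyond clarification. If the sponsor intended a single criterion, naming that one would also remove the contradiction.

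The cost is one phrase at the next amendment. A few more participants may stay off drug; they continue in follow-up and in the intention-to-treat analysis.

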7.2 PARTICIPANT DISCONTINUATION/WITHDRAWAL FROM THE STUDY

Participants are free to withdraw from participation in the study at any time upon request.

An investigator may discontinue or withdraw a participant from the study for the following reasons:

- Pregnancy
- Significant study intervention non-compliance (as determined by primary investigator)
- If any clinical adverse event (AE), laboratory abnormality, or other medical condition or situation occurs such that continued participation in the study would not be in the best interest of the participant
- Disease progression which requires discontinuation of the study intervention
- If the participant meets an exclusion criterion (either newly developed or not previously recognized) that precludes further study participation
- Participant unable to receive study drug for > 4 weeks.

Discontinuation from the study medication (vitamin E or matching placebo) does not mean discontinuation from the study and remaining study procedures should be completed as indicated by the study protocol. The reason for participant discontinuation or withdrawal from the study will be recorded on the Case Report Form (CRF). Participants who sign the informed consent form and are registered but do not receive the study intervention may be replaced. Participants who sign the informed consent form, and are randomized and receive the study intervention, and subsequently withdraw, or are withdrawn or discontinued from the study will not be replaced.

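### Section 7.2 permits withdrawal from the study for time off drug or non-compliance, 7.1 requires follow-up to continue after a permanent drug stop, and nothing says which governs

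*Combined protocol and SAP*

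**What the plan says.** Section 7.1 (discontinuation of study intervention) keeps people in the trial after the drug is stopped. For a severe or prolonged adverse event, or intolerance, "the participant will no longer receive the study medication, but will continue to be followed in the study according to the protocol", and the stated reason is the intention-to-treat principle. After the liver-injury stopping criteria it says: "Follow-up visits will continue, but the study medication will not be restarted. The participant will be included in intention-to-treat analyses".

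Section 7.2 (withdrawal from the study) opens its list with "An investigator may discontinue or withdraw a participant from the study for the following reasons". Two of the reasons concern only the participant's drug-taking: "Participant unable to receive study drug for > 4 weeks" and "Significant study intervention non-compliance (as determined by primary investigator". The others are pregnancy, the participant's best interest, disease progression that requires stopping the intervention, and an exclusion criterion that rules out further participation. The closing paragraph of 7.2 then says that discontinuing the medication "does not mean discontinuation from the study and remaining study procedures should be completed as indicated by the study protocol". It adds that treated participants who are later withdrawn are not replaced.

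On the analysis side, section 9.3 defines the intention-to-treat set as everyone randomized. Sections 9.2 and 9.4.1 make the primary analysis complete-case unless more than 10% of patients lack the primary endpoint, in which case multiple imputation is used to bring in all randomized patients.

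**The concern.** The same participant can fall under two instructions. One says follow-up continues; the other allows the investigator to end it. Two sites could handle identical cases in opposite ways, and both could cite the protocol.

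What is at stake is the week-24 ALT. Time off drug and non-compliance are consequences of treatment, so ending follow-up for those reasons makes the endpoint missing in a way that may be related to the outcome. The link is most direct for the liver-injury stops: they are triggered by ALT or AST, and ALT is the primary endpoint. If such values are lost and the analysis is complete-case, the comparison with placebo describes those who stayed on drug more than it describes everyone randomized.

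**Working it through.** **1. The passages side by side.**

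| Place | Situation | Instruction | Force |
|---|---|---|---|
| 7.1 | Permanent stop for adverse event or intolerance | Follow-up continues | mandatory (will) |
| 7.1 | Stop under liver-injury criteria | Visits continue, included in ITT | mandatory (will) |
| 7.2 list | Off drug for more than 4 weeks, or non-compliant | May be withdrawn from the study | permissive (may) |
| 7.2 closing paragraph | Medication discontinued | Remaining procedures completed | should |

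No text limits the list to cases outside 7.1 or states an order of precedence.

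**2. How far the two rules overlap.** Treatment lasts 24 weeks. A permanent stop at week t leaves 24 − t scheduled weeks without drug, which exceeds 4 when t < 20. Before week 24, treatment-phase visits fall at weeks 4, 8 and 12 (section 8.1.4). A permanent stop at one of them leaves 20, 16 or 12 weeks off drug before the week-24 visit. So most 7.1 stops before about week 20 would meet the 7.2 reason before the primary endpoint is measured. Stops after about week 20 would not.

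**3. Which analysis would then apply.** The switch to imputation is stated as one percentage of patients, with no rule by arm. Ten withdrawals in one arm are 10/50 = 20% of that arm but 10/200 = 5% of the trial. If no more than 10 other values were missing (20/200 = 10%), the analysis would remain complete-case.

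**4. The plan's own sample size, as a reference.** Inputs from section 9.2: difference 20 points, SD 31, power 90%, 10% missing. With n = 2[SD(c + z₀.₉₀)/Δ]² and a simulated Williams critical value c = 1.75 (three doses, one-sided 5%):

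- n = 2[31(1.75 + 1.282)/20]² = 44.2, so 45 evaluable per group
- 45/0.90 = 50 per group, as stated

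The match needs the one-sided 5% value although section 9.2 calls the error rate two-sided. That is a separate matter and does not affect this point.

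**5. Possible bias (assumption only).** The documents give no rate of withdrawal. Suppose a fraction w of a vitamin E arm is withdrawn, those remaining show the planned 40% change, and every withdrawn participant would have shown the placebo figure of 20%. The mean over all randomized is 40 − 20w, the completer mean is 40, and the overstatement is 20w:

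- w = 0.10 (5 of 50): 2 points, or 2/20 = 10% of the planned effect
- w = 0.20 (10 of 50): 4 points, or 4/20 = 20% of the planned effect

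**6. Possible loss of power (assumption only).** With equal loss in every arm and complete-case data, power = Φ(Δ/[SD√(2/n)] − c):

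- 10% missing, n = 45: Φ(3.06 − 1.75) = 0.905
- 20% missing, n = 40: Φ(2.89 − 1.75) = 0.872
- 30% missing, n = 35: Φ(2.70 − 1.75) = 0.828

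Above 10% overall the plan would in fact impute, so the last two lines only indicate the information lost. Sections 9.2 and 9.4.1 do not say whether drug status would enter the imputation model.

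**The case against.** The best defence is that the sections can be read together. The list in 7.2 is permissive, 7.1 is specific and mandatory, and the closing paragraph of 7.2 shows the intent. On that reading 7.1 simply governs the people it covers. This stands in part: the intention is stated twice in 7.1 and once in 7.2, and nothing in 7.2 compels a withdrawal. But the precedence has to be inferred, the list is expressly about leaving the study, and non-compliant participants are not covered by 7.1 at all.

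A second defence is that the analysis already copes, because multiple imputation applies above 10% missing and withdrawn participants remain in the intention-to-treat set. That is right as far as it goes. It does not help below the overall 10% threshold, where losses concentrated in one arm can sit. Imputation also has to stand in for values that 7.1 meant to be observed.

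Several stronger readings are tempting and do not hold:

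- That everyone stopped under 7.1 must meet the 4-week reason. Stops after about week 20 do not, and the groups only overlap: 7.1 covers particular causes, whereas 7.2 covers any inability to receive drug.
- That losses will be concentrated among poor responders at the highest dose. The documents give no withdrawal rate by dose, and section 2.3.1 describes the 800 IU dose as without significant toxicity in adults.
- That 5–10 withdrawals in one arm use up the trial's missing-data allowance. They are 2.5–5% of 200.
- That the exclusion-criterion reason is of the same kind as time off drug. It applies only where the criterion rules out further participation.

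**Conclusion.** The conflict is textual and depends on no number. Sections 7.1 and 7.2 give different answers for an overlapping group, 7.2 is at odds with its own closing paragraph, and no precedence is stated. If investigators use the permission, week-24 ALT can be lost for reasons tied to treatment, in numbers that need not trigger imputation.

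The size is unknown. The 2–4 point overstatement is a scenario. It rests on 10–20% of one arm being withdrawn, on all of them responding like placebo, and on the analysis staying complete-case. A reader might infer that the primary analysis becomes per-protocol. The documents do not support that: withdrawal is optional, the analysis set remains all randomized participants, and imputation applies above 10% missing. The supported conclusion is narrower: an avoidable, possibly site-dependent source of informative missing data that is worth closing at the next amendment.

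**What to change.** Reconcile 7.1 and 7.2 so that time off drug or non-compliance does not by itself end outcome collection. State that ALT at the week-24 visit, and later visits where the participant agrees, are collected regardless of drug status.

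This concerns data collection only. The pregnancy, disease-progression and best-interest reasons, the reason for an exclusion criterion that rules out further participation, and every decision to stop or restart drug are left to the sponsor. Deleting all reasons except withdrawn consent and loss to follow-up would go further than this point requires.

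The cost is a wording amendment and a few more attended visits, most of which 7.1 already requires. The sample size and the primary test are unchanged.
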